## Specific Aims

Maternal oxygen administration for concerning fetal heart rate tracing (FHT) patterns is common practice on Labor and Delivery units in the United States. Despite the broad use of oxygen, it is unclear if this practice is beneficial for the fetus. Category II FHT, as defined by the National Institute of Child Health and Human Development (NICHD), is a broad class of FHT patterns that may suggest cord compression and/or placental insufficiency for which oxygen is most commonly administered. Although some animal and human studies have demonstrated that maternal hyperoxygenation can alleviate such fetal heart rate decelerations, this purported benefit has not been shown to translate into improved fetal outcomes, particularly in relation to acid-base status. In fact, some studies suggest harm with oxygen use due to lower umbilical artery pH and increased delivery room resuscitation or increased free radical activity. Given the indeterminate evidence for this ubiquitously employed resuscitation technique, there is an urgent need to further study the utility of maternal oxygen administration in labor for fetal benefit.

We propose a randomized controlled non-inferiority trial comparing oxygen to room air in patients with Category II FHT. Our central hypothesis is that room air alone is not inferior to oxygen administration with regard to neonatal acid-base status and FHT and may in fact, be a safer option for resuscitation due to less production of reactive oxygen species.

**Primary Aim: Determine the effect of maternal oxygen administration for Category II FHT on arterial umbilical cord lactate.**

*Hypothesis: Room air, as a substitute for oxygen supplementation, is no different than oxygen in altering the acid-base status of the neonate as reflected in umbilical arterial (UA) lactate.*

Fetal hypo-oxygenation, as reflected by decelerations in the FHT, results in metabolic acidosis due to a shift from aerobic to anaerobic metabolism in which lactate and hydrogen ion production significantly increase causing a decrease in pH. Elevated umbilical cord lactate has been shown to be a surrogate for fetal metabolic acidosis and resultant neonatal morbidity. The primary outcome will be umbilical arterial (UA) lactate, and secondary outcomes will be other components of a UA gas.

**Secondary Aim #1: Characterize the effect of oxygen administration on fetal heart tracing patterns**

*Hypothesis: Oxygen administration will be associated with a rate of persistent Category II FHT that is not different from those exposed to room air.*

Oxygen is typically administered in response to FHT interpretation. Hence, evaluating the effect of oxygen on subsequent FHT is pivotal to labor management. The primary outcome will be resolution of Category II FHT. We will also investigate the effect of oxygen administration on mode of delivery, particularly cesarean delivery for non-reassuring fetal status.

**Secondary Aim #2: Evaluate the safety of oxygen administration by measuring reactive oxygen species (ROS) in maternal and neonatal blood.**

*Hypothesis: Oxygen administration will be associated with increased oxidative stress in maternal and neonatal cord blood as represented by malondialdehyde (MDA).*

Over-oxygenation can result in free radical or ROS formation that have detrimental downstream effects. The presence of reactive oxygen species results in degradation of lipids in the cell membrane and resultant formation of malondialdehyde (MDA), which has been studied as a surrogate for oxidative stress.

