## **Specific Aim 2: Characterize the effect of oxygen administration on fetal heart tracing patterns**

In clinical practice, oxygen is administered to patients with Category II FHT in order to resuscitate potential fetal hypooxygenation that manifests as heart rate decelerations. Evidence thus far shows that Category II FHT are associated with a wide spectrum of neonatal outcomes and therefore do not uniformly reflect fetal acid-base status. Hence, evaluating the effect of oxygen on subsequent FHT categorization is pivotal to labor management. The outcome that will be investigated is rate of persistent Category II FHT after intervention. We will also evaluate the types and frequency of deceleration patterns present both pre and post intervention. We hypothesize that oxygen administration for Category II FHT will be associated with a rate of persistent Category II FHT that is not different from those exposed to room air.

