## **Statistical Analysis**

Intention-to-treat (primary analysis) and per protocol analyses will be performed. Chi-squared and Fisher's exact tests will be used to compare categorical variables as appropriate. Continuous variables will initially be assessed for distribution pattern via the Kolmogorov-Smirnov test. Normally distributed variables will be compared using Student's t-tests and non-normally distributed variables will be analyzed with the Mann-Whitney U test. These analyses will be supplemented by multivariable logistic regressions to adjust for confounders.

Tests with  $p < 0.05$  will be considered statistically significant. Analyses will be performed using Stata (Stata Corp., College Station, TX).

For the primary outcome of lactate, 95% confidence intervals (CI) will be calculated for the mean cord lactate levels in each group. Comparison of the 95% CI in each group will then determine non-inferiority or inferiority.

Additional interaction analyses for the primary outcome will be performed for the following subgroups:

- 1) Presence of chronic medical conditions (hypertensive disorder, diabetes)

- a. Patients with hypertensive disorders (chronic hypertension, gestational hypertension, preeclampsia)
- b. Patients with diabetes mellitus (gestational diabetes, T1DM, T2DM)
- 2) Recurrent late decelerations pre intervention
- 3) Recurrent variable decelerations pre intervention
- 4) Prolonged deceleration pre intervention
- 5) Fetal tachycardia pre intervention
- 6) Fetuses with intrauterine growth restriction
- 7) Chorioamnionitis
- 8) Within oxygen group: Duration of oxygen exposure
  - a. <50% of total duration of active labor (onset of active labor to delivery)
  - b. >50% of total duration of active labor (onset of active labor to delivery)

Odds ratios and 95% CI will be calculated for the secondary outcome of persistent Category II FHT. Kaplan-Meir analyses will be performed for fetal monitoring analyses.

For the outcome of maternal and cord blood MDA, a fetal MDA will be calculated by subtracting umbilical artery MDA from maternal MDA for each sample. The calculated mean fetal MDA and maternal MDA values will then be compared between groups using either Student t test or Mann Whitney U test.

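### The plan hypothesizes no difference in persistent Category II tracings but states no criterion that could establish it, so a non-significant result could be read as support

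*Combined protocol and SAP*

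**What the plan says.** The hypothesis under Secondary Aim #1 (Specific Aims) is: "Oxygen administration will be associated with a rate of persistent Category II FHT that is not different from those exposed to room air". The Background repeats it under Specific Aim 2, again expecting a "rate of persistent Category II FHT that is not different from those exposed to room air". The opening of Specific Aims goes further and makes the tracing part of the trial's overall claim: "Our central hypothesis is that room air alone is not inferior to oxygen administration with regard to neonatal acid-base status and FHT".

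The Statistical Analysis section provides the following for this outcome:

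- a general rule that chi-squared and Fisher's "exact tests will be used to compare categorical variables as appropriate", with the threshold "Tests with $p < 0.05$ will be considered statistically significant";
- one outcome-specific sentence: "Odds ratios and 95% CI will be calculated for the secondary outcome of persistent Category II FHT";
- Kaplan-Meier "analyses will be performed for fetal monitoring analyses".

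The section's one non-inferiority rule, "Comparison of the 95% CI in each group will then determine non-inferiority or inferiority", belongs to the lactate outcome. The 30% margin, the one-sided alpha of 0.025 and the 90% power under Sample size analysis are also for lactate. For persistent Category II the documents give no expected rate, margin, equivalence or non-inferiority criterion, or power.

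**The concern.** A hypothesis of no difference, or of non-inferiority, needs a stated limit on how much worse room air could be, and a rule that compares the confidence interval with that limit. The plan has both for lactate and neither for the tracing. The only decision threshold that reaches this outcome is p<0.05 on a test of difference, and failing to reach it does not show that the rates are alike.

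The Background says that evaluating the effect on the tracing is central to managing labor. It also cites work in which maternal hyperoxygenation relieved decelerations, so worse tracings on room air are a possibility the protocol itself recognizes. The section on significance and impact says that room air may be equally effective if the hypothesis is borne out. An uninformative null on the tracing could lend that statement weight it has not earned.

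**Working it through.** **Inputs from the documents.** 114 patients are analyzed after the 6 run-in patients are set aside (Sample size analysis), with 1:1 allocation (Strategy). That gives 114/2 = 57 per arm. Lactate: mean 3.5, SD 1.6 mmol/L, margin 30%, one-sided alpha 0.025, power 90%.

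**Assumptions.** The documents give no persistence rate, so 30%, 50% and 70% on oxygen are used. True rises of 10, 15 and 20 points under room air are also assumed, and none is offered as a clinically agreed threshold. The p<0.05 rule is taken as two-sided because its sidedness is not stated.

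**1. The plan's own figure (lactate).** Margin = 0.30 × 3.5 = 1.05. n per arm = 2 × 1.6² × (1.960 + 1.282)² / 1.05² = 48.8, so 49 per arm and 98 in total, as stated. The noncentral-t version gives 100. This calculation contains nothing about the tracing.

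**2. Precision when the observed rates are equal, n = 57 per arm.**

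- Odds ratio: exp(±1.96 × √[2/(np) + 2/(n(1−p))]). At p = 0.5 this is exp(±1.96 × 0.375) = 0.48 to 2.08. At p = 0.3 or 0.7 it is exp(±1.96 × 0.409) = 0.45 to 2.23.
- Risk difference: ±1.96 × √[2p(1−p)/n]. At p = 0.5 this is ±18.4 points. At p = 0.3 or 0.7 it is ±16.8 points.

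**3. How often a true rise d would be non-significant.** Power = Φ[(d − 1.96 × SE₀)/SE₁], where SE₀ uses the pooled rate and SE₁ the separate rates. Example at 50% against 65%: SE₀ = √(2 × 0.575 × 0.425/57) = 0.0926 and SE₁ = √[(0.25 + 0.2275)/57] = 0.0915. Power = Φ[(0.15 − 0.1815)/0.0915] = Φ(−0.344) = 0.365, so 63% of trials are non-significant.

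| True rise under room air | 30% on oxygen | 50% on oxygen | 70% on oxygen |
|---|---|---|---|
| 10 points | 80% | 81% | 77% |
| 15 points | 62% | 63% | 52% |
| 20 points | 41% | 41% | 23% |

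Exact enumeration of the chi-squared test gives 76–82%, 51–64% and 21–41% for the three rows. The smallest rise detectable with 80% power is about 21 to 26 points.

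**4. What a margin would require.** With equal true rates, one-sided 0.025 and 90% power, n per arm = (1.960 + 1.282)² × 2p(1−p)/margin². The margins are illustrative.

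| Margin | n per arm at 50% (at 30% or 70%) | Power with 57 per arm at 50% (at 30% or 70%) |
|---|---|---|
| 10 points | 526 (442) | 19% (21%) |
| 15 points | 234 (197) | 36% (42%) |
| 20 points | 132 (111) | 57% (64%) |

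**The case against.** The strongest reply is that this is a secondary aim whose title is to characterize an effect, and that its outcome-specific analysis is already estimation: an odds ratio with a confidence interval, plus Kaplan-Meier analyses. The chi-squared and p<0.05 sentences are generic. An interval of about 0.45 to 2.2 would show any careful reader how little had been excluded. Margins for secondary outcomes are often absent, and the impact statement is conditional and rests mainly on acid-base status.

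Much of this stands, and it rules out three stronger readings that a reader might infer:

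- *That the plan offers only a significance test here.* It does not. The odds ratio with 95% CI and the Kaplan-Meier analyses are planned.
- *That the plan treats non-significance as confirmation.* It never says so. That reading is an inference, open because no other criterion is stated.
- *That a null result is likely whether or not room air is worse.* This depends on the size of the rise. A 20-point rise would be missed in 23–41% of trials and a 25-point rise in 5–22%. Even at 15 points from a 70% base, the figure is close to one half.

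The reply does not remove the gap. An interval without a margin gives no rule for concluding that rates are alike or that room air is not inferior, and the Specific Aims put the tracing inside the central non-inferiority claim.

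**Conclusion.** The concern holds in this form: the hypothesis of no difference in persistent Category II tracings, and the tracing part of the central non-inferiority hypothesis, have no stated criterion that could establish them. A non-significant result could be read as support although it would leave differences of up to about 17 to 18 points open in either direction when observed rates are equal. These sizes rest on the assumed persistence rates and rises, a two-sided 5% test, and outcome data from all 57 patients per arm. Fewer evaluable patients would widen the intervals. The point is about what the trial can conclude on a secondary outcome. Lactate has its own margin, power and rule, and this point does not touch them.

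**What to change.** Restate the tracing hypothesis as estimation wherever it appears. In Statistical Analysis, add the risk difference (room air minus oxygen) with 95% CI to the odds ratio already planned, and state that p≥0.05 will not be taken as showing the rates to be no different or room air to be non-inferior. Bring the central hypothesis into line with this.

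If a non-inferiority claim on the tracing is wanted, prespecify and justify a risk-difference margin before any results are seen, and require the upper 95% limit to lie below it. A claim of no difference in both directions would also need the lower limit to lie above minus the margin.

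The cost is wording in the aims and a sentence or two in the analysis section, with no extra patients or data. The downside is a weaker secondary claim, because 57 per arm is underpowered for modest margins.

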## Background/Significance

Maternal oxygen administration for fetal heart rate tracing (FHT) changes is a common practice on Labor and Delivery units in the United States. Despite the broad use of oxygen for intrauterine resuscitation of fetal heart rate decelerations, it is unclear if this practice is beneficial for the fetus. In a recent review of maternal oxygen administration in labor, Hamel et al concluded that there is insufficient evidence for routine oxygen administration for intrauterine resuscitation and that such administration may even be harmful via production of free radicals. The 2012 Cochrane review evaluating maternal oxygen administration for fetal distress also found limited evidence to evaluate the effectiveness of oxygen for fetal distress.

Category II FHT, as defined by the National Institute of Child Health and Human Development (NICHD), is a broad class of FHT patterns which can include both variable and/or late decelerations, representing cord compression and placental insufficiency, respectively. These decelerations are often thought to be a reflection of fetal hypooxygenation. The underlying hypothesis for oxygen benefit and the primary motivation for generalized use in labor is to transfer oxygen to the fetus and therefore improve or reverse the perceived fetal hypooxygenation determined by the FHT.

Although some animal and human studies have demonstrated that maternal hyperoxygenation can alleviate fetal heart rate decelerations and increase fetal oxygen saturation, this purported benefit has not been shown to translate into improved fetal outcomes, particularly in relation to acid-base status. For example, a study in primates by Morishima et al demonstrated that maternal oxygen administration to those with acidotic hypoxic fetuses elevated fetal oxygen levels and eliminated late decelerations but did not correct acidosis.

There are a limited number of clinical trials addressing maternal oxygen administration for fetal distress in labor. In 1995, Thorp et al conducted a randomized trial of oxygen versus room air in the second stage of labor, and found no benefit to oxygen exposure and in fact discovered that the oxygen group had a lower umbilical artery pH. This difference was theorized to be a result of fetoplacental vasoconstriction as a result of prolonged oxygen exposure. Similarly, Nesterenko et al performed a trial of laboring women randomized to oxygen or room air and found that more infants in the oxygen group required delivery room resuscitation. Excess oxygen exposure in this setting has also been linked with increased free radical activity. In a 2002 trial by Khaw et al,

women were randomized to oxygen or room air during cesarean delivery. There was no difference in umbilical artery pH between groups, however the oxygen exposed group had increased free radical activity in cord blood samples. Studies such as these have prompted questioning of both the safety and the efficacy of oxygen for Category II FHT and highlight the urgent need for further investigation, particularly given its wide-spread use.

The primary objective of this study is to evaluate whether oxygen for intrauterine fetal resuscitation of Category II FHT affects fetal metabolic acid-base status as determined by umbilical cord lactate values. Secondary objectives include analysis of additional cord gas parameters used to predict neonatal wellbeing, changes to FHT patterns, and cord blood and maternal MDA as a marker of free radical activity. We hypothesize that room air exposure for Category II FHT in labor is no different from maternal oxygen administration with regard to fetal acid-base status.

**Specific Aim 1: Determine the effect of maternal oxygen administration for Category II FHT on arterial umbilical cord lactate.** Fetal hypooxygenation, as reflected by decelerations in the FHT, results in a metabolic acidosis due to a shift from aerobic to anaerobic metabolism in which lactate and hydrogen ion production significantly increases as a result of glucose breakdown and pyruvate conversion. This rise in lactate results in decreased pH or an acidotic state. Elevated umbilical cord lactate has been shown to be a surrogate for metabolic acidosis in the fetus and is associated with neonatal morbidity. It has also been shown to precede pH changes in the setting of hypooxygenation.

The theorized benefit of maternal oxygen administration is increase oxygen delivery to the fetus via the umbilical cord vein (Figure 1) resulting in prevention or reversal of anaerobic metabolism and a subsequent reflection in umbilical cord artery findings. This, however, has not been substantiated by evidence thus far. We hypothesize that room air, as a substitute for oxygen supplementation, is no different than oxygen in altering the acid-base status of the neonate as reflected in umbilical cord gas parameters. Secondary outcomes will be additional components of an umbilical artery gas.

[figure not shown]

Figure 1: Fetoplacental circulation

## **Specific Aim 2: Characterize the effect of oxygen administration on fetal heart tracing patterns**

In clinical practice, oxygen is administered to patients with Category II FHT in order to resuscitate potential fetal hypooxygenation that manifests as heart rate decelerations. Evidence thus far shows that Category II FHT are associated with a wide spectrum of neonatal outcomes and therefore do not uniformly reflect fetal acid-base status. Hence, evaluating the effect of oxygen on subsequent FHT categorization is pivotal to labor management. The outcome that will be investigated is rate of persistent Category II FHT after intervention. We will also evaluate the types and frequency of deceleration patterns present both pre and post intervention. We hypothesize that oxygen administration for Category II FHT will be associated with a rate of persistent Category II FHT that is not different from those exposed to room air.

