Consent will be obtained at time of admission to Labor & Delivery. Randomization to either the oxygen group or room air group will be performed when the patient is in active labor (defined as regular contractions and  $\geq 6$  cm cervical dilation) and develops Category II FHT necessitating intrauterine resuscitation as determined by the care provider team (Figure 3). This will be performed via a computer-generated randomization sequence in a 1:1 ratio. Patients randomized to the oxygen group will receive the above stated current management of oxygen via nonrebreather face mask at 10L/min and “per-protocol” defined as receiving the mask for at least 90% of the remaining duration of labor including during cesarean delivery. Patients randomized to the room air group will not receive oxygen for Category II FHT unless otherwise required for maternal indications. Alternative and/or additional intrauterine resuscitation techniques for both groups (i.e. fluid bolus, maternal repositioning, and discontinuation of oxytocin) will be left to

the discretion of the medical team. The initial 6 patients consented and randomized will be part of a compliance run-in with the same protocol as above.

[figure not shown]

Figure 3: Flow diagram for randomization and treatment groups  
 L&D: Labor and Delivery FHT: fetal heart tracing

Specific Aim 1: Determine the effect of maternal oxygen administration for Category II FHT on neonatal cord gas parameters

After delivery of the infant, a segment of the umbilical cord will be removed with immediate collection of umbilical artery and vein samples by trained providers. These samples will be sent to the hospital laboratory for routine cord gas measurements as is universally practiced on our Labor and Delivery unit.

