#### Specific Aim 2: Characterize the effect of oxygen administration on fetal heart tracing patterns

The patient's primary nurse will document the time at which intervention is initiated. A blinded investigator will then retrospectively assess FHT categorization and deceleration patterns both pre and post intervention.

Specific Aim 3: Evaluate the safety of oxygen administration by measuring ROS in maternal and neonatal blood

We will be measuring serum MDA in both cord and maternal blood as a marker of oxidative stress. MDA is a byproduct of lipid peroxidation, which occurs as a result of oxidative stress. Measurement of Thiobarbituric Acid Reactive Substances (TBARS) is a commonly used assay

for quantifying MDA This assay is performed by fluorometrically measuring the MDA-TBA complex formed in plasma or serum by the reaction of MDA and TBA.

Upon delivery of the infant, an additional sample of umbilical artery blood will be collected for this analysis. An optional sample of maternal blood will also be drawn within 60 minutes of delivery. Both blood samples will be centrifuged to collect plasma which will then be stored at -80°C until the TBARS assay is performed.

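### Deceleration types and frequency have no window, unit or baseline adjustment, so the default tests give up precision and would be open to bias if raw counts to delivery were used

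*Combined protocol and SAP*

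**What the plan says.** Background/Significance, Specific Aim 2, names persistent Category II tracing as the outcome and then adds: "We will also evaluate the types and frequency of deceleration patterns present both pre and post intervention". Strategy, Specific Aim 2, gives the measurement: "A blinded investigator will then retrospectively assess FHT categorization and deceleration patterns both pre and post intervention". Neither section states how long either segment is, whether frequency is a count, a rate or a proportion, or which contrast will be drawn.

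A woman is randomized once she is in active labor and "develops Category II FHT necessitating intrauterine resuscitation as determined by the care provider team". Per-protocol oxygen means "receiving the mask for at least 90% of the remaining duration of labor including during cesarean delivery". The time from randomization to delivery therefore differs from woman to woman.

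Statistical Analysis names no method for deceleration patterns. Its general rules are "Chi-squared and Fisher's exact tests will be used to compare categorical variables as appropriate" and "Normally distributed variables will be compared using Student's t-tests and non-normally distributed variables will be analyzed with the Mann-Whitney U test". It adds supplementary multivariable logistic regression for unnamed confounders, odds ratios for persistent Category II tracing, and Kaplan-Meier analyses for fetal monitoring with no event, time origin or censoring rule. Pre-intervention patterns appear there only as subgroups for lactate.

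**The concern.** Two separate matters are left open.

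**Time.** The number of decelerations on a strip, and the chance of seeing a given type at all, grow with strip length. If the reader counts to delivery and the default tests are applied, variation in strip length between women adds noise. If one arm is also delivered sooner, that arm shows fewer decelerations even at the same hourly rate. Such a difference is possible: no sham is described, only the retrospective reader is called blinded, and the protocol itself treats cesarean for non-reassuring fetal status as something oxygen may affect.

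**Baseline.** The same measure is read before the intervention, but no analysis of this endpoint uses it. In a randomized comparison this does not bias the result. It discards precision that costs nothing to recover. A within-arm before/after change would not be a substitute, because every woman enters when her tracing is abnormal, so both arms would tend to improve.

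**Working it through.** **Figures in the plan.** None is given for this endpoint. The only sample size is for lactate (Sample size analysis): SD 1.6, margin 30% of 3.5 = 1.05, one-sided alpha 0.025, power 90%. n per arm = 2 × (1.96 + 1.2816)² × 1.6² / 1.05² = 48.8, so 49, or 98 in total, as stated. After the drop-out allowance the plan analyses 114 women, 57 per arm at 1:1. The checks below use 57.

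**Assumptions.** Deceleration rates, their spread and strip lengths are not in the documents. Two assumed models were simulated, with tests at two-sided 0.05.

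**Model 1: does unequal time bias a raw count?** Assumed: 6 decelerations per hour in both arms, gamma heterogeneity (shape 2), gamma strip time (shape 1.5, mean 2 h) plus 0.1 h, 4000 runs. Expected count = rate × mean time = 6 × 2.1 = 12.6 in the reference arm. With time scale q in the other arm, the expected count ratio is (2q + 0.1)/2.1.

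| q | Expected ratio | Simulated ratio | Mann-Whitney, raw counts | Mann-Whitney, per hour |
|---|---|---|---|---|
| 1.0 | 1.000 | 1.000 | 4.7% | 4.8% |
| 0.9 | 0.905 | 0.903 | 7.2% | 5.1% |
| 0.8 | 0.810 | 0.811 | 14.3% | 5.0% |
| 0.7 | 0.714 | 0.717 | 27.7% | 4.7% |
| 0.6 | 0.619 | 0.621 | 50.9% | 5.2% |

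The first row matters as much as the last: with equal time in the two arms, the raw count keeps its nominal error rate.

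**Model 2: power, and the separate parts of the gain.** Assumed: 8 per hour, between-woman log-SD 0.6 shared before and after, exponential strip time with mean 2 h, 30-minute pre-intervention strip, about 1500 runs. The adjusted analysis regresses the log rate on arm and pre-intervention log rate, with robust standard errors. Ranges are from repeated runs.

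- True rate 40% higher on room air, equal time: raw-count t-test 26-27%, raw-count Mann-Whitney 26-30%, unadjusted rate 64-67%, adjusted rate 76-81%. Most of the gain comes from the time denominator and the rest from baseline.
- The same, with an equal 30-minute window in both arms: unadjusted about 60% in one run, rising to 71% with baseline adjustment. Another run gave 64% unadjusted, with 4.8% type I error. Here only baseline matters.
- Rate 40% higher and 25% shorter time on room air: raw counts 4-7%, adjusted rate 74-77%.
- Equal rates, one arm 25% shorter: raw counts 17-21% false positives, adjusted rate 5-6%. At 10% shorter, raw counts give 6-7%.

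**Baseline adjustment in general.** Residual variance is multiplied by 1 − r². For assumed r = 0.3, 0.5 and 0.7 this is 0.91, 0.75 and 0.51, so 114 women carry the information of 114/0.91 = 125, 114/0.75 = 152 and 114/0.51 = 224.

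**Limit of a whole-strip rate.** Model 2 holds each woman's rate constant and makes strip time independent of the tracing. If instead the rate doubles or triples in the last 30 minutes, with equal true rates and 25% sooner delivery in one arm, the adjusted whole-strip rate rejects in 8.4% or 10.8% of trials. At 40% sooner delivery it rejects in 13% or 25%. Dividing by time to delivery is therefore not fully protective.

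**The case against.** The best reply is that this is an unspecified secondary analysis, not a wrong one. No section says that raw counts to delivery will be compared. Frequency can mean a rate or a fixed-window count, and the subgroup list treats patterns as categories. The phrase about the remaining duration of labor describes the mask, not the reader's window. Statistical Analysis also assigns a time-based method, Kaplan-Meier, to fetal monitoring. All of that stands, and it rules out two stronger readings. A reader might infer that the plan has chosen a biased raw-count test, but the documents do not say so. A reader might also infer that no time-based or adjusted method is named, and that is incorrect.

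It does not close the gap. Kaplan-Meier without an event or origin yields no deceleration frequency, logistic regression does not model a count over time, and neither is said to use the pre-intervention reading.

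It is also correct that bias needs a between-arm difference in time to delivery, which the documents do not quantify, and that variation between women alone only adds noise. Finally, monitored time to delivery arises after randomization, so a whole-strip offset model needs its own justification. That point shapes the fix.

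**Conclusion.** The point holds as a precision gain that costs nothing, plus protection against a conditional bias. As written, the plan leaves the window and the unit of frequency open, and its default tests ignore both monitored time and a baseline value already collected.

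- If frequency is a raw count to delivery, power falls substantially (about 26-30% against 76-81% in the assumed case), and a 25% difference in time to delivery would produce about 17-21% false positives. A 10% difference would produce about 6-7%.
- If a rate or fixed window is meant, the loss is only the baseline precision: about 60% against 71% power in the assumed fixed-window case.

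These sizes rest entirely on assumed rates, heterogeneity and strip lengths. A reader might go further and conclude that harm from withholding oxygen would be hidden. The documents do not support that: cord lactate, other cord gas values and cesarean for non-reassuring fetal status are also planned outcomes. The deceleration endpoint is secondary, and the lactate conclusion does not depend on it.

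**What to change.** In Statistical Analysis, add a paragraph for deceleration patterns:

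1. Count each pattern in a common fixed window before and after randomization, with the window length set before any strip is read. State the rule for delivery before the window ends, using log monitored minutes within the window as offset.
2. Compare arms with a negative-binomial model for frequency, or a logistic model for presence of a type. Include treatment arm and the pre-intervention value of the same pattern as covariate.
3. Base the conclusion on the between-arm contrast, not on change within an arm.
4. Report the rate over the whole strip to delivery only as a sensitivity analysis, because strip length is a post-randomization quantity.
5. For the Kaplan-Meier analyses, define the event, the time origin and the handling of delivery.

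The cost is wording and a little more analysis work: tracings, intervention start times and the blinded reading of both segments are already planned. The downside is that a fixed window ignores later tracing, which the sensitivity analysis partly recovers. Sample size does not change.
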